11.9.3. Visit 3 (Week 1; Day 8 + 2 days) – Treatment Period

The following procedures will be conducted during this visit:

- Collect concomitant medications
- Vital sign measurements
- Blood sample POPPK
- PANSS
- CGI-S
- CGI-I
- C-SSRS
- Collect adverse events
- Study drug accountability
- Dispense study drug

11.9.4. Visit 4 (Week 2; Day 15 ± 2 days) – Treatment Period

The following procedures will be conducted during this visit:

- Collect concomitant medications
- Vital sign measurements
- PANSS
- CGI-S
- CGI-I
- C-SSRS
- Collect adverse events
- Study drug accountability
- Dispense study drug

11.9.5. Visit 5 (Week 3; Day 22 ± 2 days) – Treatment Period

The following procedures will be conducted during this visit:

- Collect concomitant medications
- Vital sign measurements
- C-SSRS
- Collect adverse events
- Study drug accountability
- Dispense study drug

11.9.6. Visit 6 (Week 4; Day 29 ± 2 days) – Treatment Period

The following procedures will be conducted during this visit:

- Collect concomitant medications
- Vital sign measurements
- Weight and waist circumference (BMI derived in the electronic data system)
- Blood sample for POPPK
- Urine sample for β hCG (for female subjects) and UDS
- PANSS
- CGI-S
- CGI-I
- BNSS
- PSQI
- C-SSRS
- Collect adverse events
- Study drug accountability
- Dispense study drug

11.9.7. Visit 7 (Week 5; Day 36 \pm 2 days) – Treatment Period

The following procedures will be conducted during this visit:

- Collect concomitant medications
- Vital sign measurements
- C-SSRS
- Collect adverse events
- Study drug accountability
- Dispense study drug

11.9.8. Visit 8 (Week 6; Day 43 \pm 2 days) – Treatment Period

The following procedures will be conducted during this visit:

- Collect concomitant medications
- Vital sign measurements
- PANSS
- CGI-S
- CGI-I
- C-SSRS
- Collect adverse events

- Study drug accountability
- Dispense study drug

11.9.9. Visit 9 Telephone Contact (Week 7; Day 50 ± 2 days) – Treatment Period

The following procedures will be conducted during this visit:

- Collect concomitant medications
- C-SSRS
- Collect adverse events

11.9.10. Visit 10, End of Treatment (EOT) or Early Termination (ET) - (Week 8; Day 57 ± 2 days)

The following procedures will be conducted during this visit:

- Collect concomitant medications
- Collect nicotine use information
- Physical and neurological examination
- Vital sign measurements
- Weight and waist circumference (BMI derived in the electronic data system)
- Perform standard 12-lead ECG
- Fasted blood samples for clinical laboratory evaluation (hematology and serum chemistry) and β -hCG (for female subjects)
- Blood sample for POPPK
- Urine sample for urinalysis, rapid urine β -hCG (females), rapid urine drug screen, and UDS
- PANSS
- CGI-S
- CGI-I
- BNSS
- PSQI
- C-SSRS
- SAS
- BARS
- AIMS
- SF-12
- MSQ

- PSP
- HCRU (since last visit)
- Collect adverse events
- Study drug accountability
- Duplicate subject check

At this visit, subjects who have participated throughout the duration of the Treatment Period, up to and including Week 8 will have the option to enroll and continue treatment in an open-label extension study (Study SEP361-309).

For subjects entering the extension study, the Week 8 Visit in this study (SEP361-308) will serve as the OLE Baseline visit for the extension study (SEP361-309) and subjects will not need to return for further visits in this study.

Subjects who do not enter the extension study will complete the Follow-up Period.

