- j. BMI will be calculated and recorded in the eCRF by the clinical site at screening. For other visits, BMI will be derived in the EDC system.
- k. Subjects must be fasted (no food or drink except water at least 8 hours prior to specified blood tests) at Pre-switch Baseline (Visit 2) and Week 8/EOT/ET (Visit 10). Fasting for 8 hours prior to Screening (Visit 1) is also recommended to avoid potential retests. Blood samples should be drawn in the morning followed by a snack or meal. A list of clinical laboratory tests is provided in [Section 23](#).
- l. Blood samples for follicle stimulating hormone (FSH) will be collected for post-menopausal women or if menopause is suspected.
- m. Any positive urine β -hCG test should be confirmed by a serum β -hCG test.

C [REDACTED] **C** [REDACTED] Blood samples for determination of plasma SEP-363856 concentrations will be collected predose (prior to administration of the first dose) on Day 1; 3 additional samples will be collected on Days 8, 29 and 57/ET. The time and date of the previous dose of study drug and the time and date of blood sampling must be recorded. The remaining plasma samples, after PK measurement is completed, **CCI** [REDACTED].

- p. Positive urine drug screen (UDS) results should be discussed with the Medical Monitor.
- q. Unscheduled SAS, BARS and AIMS scales should be administered if a subject develops extrapyramidal symptoms (EPS) requiring treatment.
- r. Healthcare resource utilization questions are described in [Section 11.5.8](#). Baseline will have 3-month lookback period. Week 8/ET will be since last assessment.
- s. Events occurring prior to first dose of study drug are pretreatment events. Events occurring after first dose of study drug are adverse events. Determination done programmatically.
- t. Where local regulations allow, duplicate subject check will be performed. Following the last contact with a subject, the duplicate enrollment system should be updated, as appropriate.

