11.5.8. Healthcare Resource Utilization

Healthcare resource utilization will be assessed by recording the following at Baseline:

- Number of physician office visits, emergency room visits, and hospitalizations (total number and number related to schizophrenia) in the previous 3 months
- Length of each hospital stay in the past 3 months
- Employment status in the past 3 months
- The average number of hours a caregiver(s) spends helping the subject per week (past 3 months)

Healthcare resource utilization will be assessed by recording the following post Baseline:

- Number of physician office visits, emergency room visits, and hospitalizations (total number and number related to schizophrenia) since prior assessment
- Length of each hospital stay since prior assessment
- Employment status since prior assessment
- The average number of hours a caregiver(s) spends helping the subject per week (since prior assessment)

[figure not shown]

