11.9.2. Pre-switch (PS) Baseline: Visit 2 (Day 1) – Treatment Period

The following procedures will be conducted during this visit:

CCI

- Review inclusion and exclusion criteria
- Collect concomitant medications
- Vital sign measurements
- Weight and waist circumference (BMI derived in the electronic data system)
- Perform standard 12-lead ECG
- Fasted blood samples for clinical laboratory evaluation (hematology and serum chemistry)
- Blood sample for POPPK

CCI

- Urine sample for urinalysis, UDS, and β hCG (for female subjects)
- PANSS
- CGI-S
- BNSS
- PSQI
- C-SSRS
- SAS
- BARS
- AIMS
- SF-12
- MSQ
- PSP
- HCRU (last 3-month lookback)
- Collect adverse events (Note: events occurring prior to first dose [on Day 1] of study drug will be identified programmatically as pretreatment events.)
- Dispense study drug

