15.3.6.1. Healthcare Resource Utilization

The number of physician's office visits, ER visits, and hospitalizations (for any reason and those related to schizophrenia) per month at Baseline and at Week 8, as well as the average length of hospital stays (for any reason and those related to schizophrenia), will be summarized. The frequency and percentage of subjects receiving unpaid care at each time point, along with the average number of hours a caregiver spends per week helping the subject, will also be summarized.

The change in the number of physician's office visits, ER visits, and hospitalizations, the average length of hospital stays, and the average number of hours a caregiver spends per week helping the subject from Baseline at Week 8 will be summarized. Shifts from Baseline to Week 8 in whether the subjects receive unpaid care will also be summarized.

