16.8. HEALTHCARE RESOURCE UTILIZATION

Healthcare resource utilization is assessed at these study visits: Visit 2 and Visit 10.

The number of physician's office visits, ER visits, and hospitalizations (for any reason and those related to schizophrenia) per month at Baseline and at Week 8/Visit 10, as well as the average length of hospital stays (for any reason and those related to schizophrenia) at Baseline and at Week 8/Visit 10, will be summarized. The frequency and percentage of subjects receiving unpaid care at Baseline and at Week 8/Visit 10, along with the average number of hours a caregiver spends per week helping the subject, will also be summarized.

The change in the number of physician's office visits, ER visits, and hospitalizations, the average length of hospital stays, and the average number of hours a caregiver spends per week helping the subject from Baseline at Week 8/Visit 10 will be summarized.

Shift from Baseline to Week 8/Visit 10 in whether the subjects receive unpaid care will also be summarized.

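### The Visit 10 procedure list anchors HCRU recall at the last visit, while Table 2 and Section 11.5.8 anchor it at the Baseline assessment; followed literally, the list covers about 7 of 56 days

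*Protocol*

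**What the plan says.** HCRU is scheduled twice. SAP Section 16.8 states: "Healthcare resource utilization is assessed at these study visits: Visit 2 and Visit 10". At Visit 2 the procedure list in Protocol Section 11.9.2 gives the recall period as "HCRU (last 3-month lookback".

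The recall period for the second assessment is described in three places:

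- Table 2, footnote r (repeated in SAP Appendix 11): "Week 8/ET will be since last assessment".
- Protocol Section 11.5.8, for the visit and admission counts: "hospitalizations (total number and number related to schizophrenia) since prior assessment". Length of stay, employment status and caregiver hours use the same anchor.
- Protocol Section 11.9.10, in the Visit 10 procedure list: "HCRU (since last visit".

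The visit just before Visit 10 is "Visit 9 Telephone Contact (Week 7; Day 50 ± 2 days". Its procedure list covers concomitant medications, the C-SSRS and adverse events, and has no HCRU item.

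For analysis, Protocol Section 15.3.6.1 and SAP Section 16.8 summarize counts of office visits, ER visits and hospitalizations "per month at Baseline and at Week 8", together with the change from Baseline. Neither document gives the number of days to use when turning a Week 8 count into a monthly figure.

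**The concern.** The two anchors are not equivalent. The last assessment of HCRU is Day 1. The last visit is a phone call one week before the end of treatment or, for an early terminator, usually the preceding weekly visit. The protocol also uses the last-visit idea literally elsewhere: Section 11.4.6.4 assigns the version of the C-SSRS with that recall period from Visit 2 onward, and the C-SSRS is done at Visit 9. Staff at Visit 10 would correctly count from Visit 9 for that scale, and could easily do the same for HCRU.

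If they did, an ER visit in Week 3 would not enter HCRU, and no other HCRU visit would pick it up. The Week 8 counts are then set against a 3-month Baseline. In a single-group study there is no control arm in which the same shortfall would show up, so an artificial drop in use after the switch could be taken for a benefit.

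**Working it through.** The documents state no figure for how much of the treatment period HCRU covers, so there is nothing to reproduce. The check is day arithmetic on the visit schedule.

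**Inputs**

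- Visit 2: Day 1 (Section 11.9.2).
- Visit 9: Day 50 ± 2 (Section 11.9.9).
- Visit 10: "Visit 10, End of Treatment (EOT) or Early Termination (ET) - (Week 8; Day 57 ± 2 days" (Section 11.9.10).

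**Length of recall on the nominal schedule**

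- Since the prior HCRU assessment: 57 − 1 = 56 days.
- Since the last visit, taken literally: 57 − 50 = 7 days.
- Share covered: 7/56 = 12.5%. Share not covered: 49/56 = 87.5%.

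**Across the visit windows**

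- Shortest: 55 − 52 = 3 days. Share not covered: (52 − 1)/(55 − 1) = 51/54 = 94.4%.
- Longest: 59 − 48 = 11 days. Share not covered: (48 − 1)/(59 − 1) = 47/58 = 81.0%.

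**Other readings of the last visit**

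- Last in-clinic visit (Visit 8, Day 43): (43 − 1)/56 = 42/56 = 75% not covered.
- Early terminators, with assumed termination days and nominal weekly visits: on Day 10 (last visit Day 8), 7/9 = 78% not covered; on Day 46 (last visit Day 43), 42/45 = 93%.

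**Effect on the monthly rate**

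Let the true event rate be r per day, unchanged from Baseline and spread evenly over treatment. The expected count in a 7-day recall is 7r.

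- Divided by 56 days: 7r/56 = r/8, so the rate is understated by 1 − 1/8 = 87.5%.
- Divided by the 7 days actually recalled: 7r/7 = r, so there is no expected bias. If the counts behave roughly as Poisson, the standard error of a rate over T days is √(r/T). It therefore grows by √(56/7) = √8 ≈ 2.8.

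The size of the distortion thus depends on two things the documents do not settle: which recall period was used, and which divisor will be applied.

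**The case against.** The protocol itself suggests which text should govern. Section 11.9 opens by sending sites to Sections 11.1 to 11.7 for how assessments are conducted. Section 11.5.8 falls in that range, Table 2 footnote r agrees with it, and the SAP schedule repeats the footnote. The entry in 11.9.10 may be no more than a short label, parallel to the one at Visit 2 and meaning the last HCRU visit. HCRU is also captured on the electronic vendor system (Table 6; tablet use is described in Section 11.9), and the prompt there probably decides the recall period in practice. All of this stands. It makes the loss conditional, but it does not remove the contradiction.

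A reader might infer more than the documents support:

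- *That seven-eighths of the HCRU data are lost.* This holds only where the literal wording was followed. The number of such sites could be none, and for the same reason it cannot be said that sites' data are unfit to pool.
- *That utilization will appear about 87% lower.* This also needs a 7-day count divided by 56 days, and no divisor is stated.
- *That length of stay and caregiver time would fall too.* The planned summaries are average length of stay and average hours per week. A shorter recall captures fewer stays, but it does not by itself shorten the average stay or scale a weekly average.
- *That mid-study hospitalizations would vanish from the trial.* Hospitalization is a seriousness criterion (Section 12.1.2) and adverse events are collected at every visit. Admissions for new or worsening events should therefore still be recorded as SAEs. Office visits, ER visits that are not serious events, and previously scheduled admissions lack that backup.

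**Conclusion.** The inconsistency is real and should be corrected. One instruction, followed as written, leaves most of the treatment period out of the office-visit, ER-visit and hospitalization counts. Only the other instruction fits a schedule with HCRU at Visits 2 and 10 alone. On the nominal schedule the literal reading covers 12.5% of the intended period (3 to 11 days across the windows).

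The understatement of about 87% in the monthly rate is a conditional figure. It assumes the short recall was used, the full 8 weeks was the divisor, and events were evenly spread at an unchanged rate. With a divisor matched to the recall, the cost is mainly precision. How many sites or subjects are affected cannot be told from the documents.

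The consequence is limited to an other endpoint that is summarized descriptively. The primary and secondary endpoints and the sample size are unaffected.

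**What to change.** 1. In Protocol Section 11.9.10, change the entry to *HCRU (since the Visit 2 Baseline assessment)*, so that it matches footnote r and Section 11.5.8.
2. Confirm the recall wording shown on the Visit 10/ET form, both on the tablet and on any paper fallback.
3. SAP Section 3.4 reports 101 subjects enrolled, so rewording the protocol may change little of the collection. The more useful step now is in SAP Section 16.8. State the recall wording actually used, and define the per-month denominator for each subject as the days from Visit 2 to the Visit 10/ET assessment, or the actual recall period if the form used a shorter one. Do this before presenting any change from Baseline. A subject-level denominator is also needed because SAP Section 6.4 maps early-termination data to the next visit at which the assessment was due. For HCRU that is Week 8, so shorter follow-up enters the same summary.

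The cost is a one-line protocol correction, a check of the form and a short SAP addition. No visit or assessment is added.

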11.9.11. Visit 11 (7 ± 2 days after last dose) - Follow-up Period

All subjects who discontinue early or do not elect to enroll in the open-label extension study (Study SEP361-309) will have a safety Follow-up Visit 7 ± 2 days after their last dose of study drug. While every effort should be made to complete the Follow-up Visit in the clinic, administration of C-SSRS, and collection of AEs and concomitant medications may occur by telephone contact if the subject is unable to come to the clinic for the Follow-up Visit.

The following procedures will be conducted during this visit:

- Concomitant medications
- Physical and neurological examinations
- Vital sign measurements
- Urine sample for β hCG (for female subjects)
- C-SSRS
- Adverse events

11.9.12. Unscheduled Visit for Dose Adjustment

If a dose increase or decrease is needed between regularly scheduled visits, the subject must return to the clinic for an unscheduled visit. The following procedures will be conducted during this visit for dose adjustment:

- Study drug accountability
- Dispense study drug
- Adverse event monitoring
- Concomitant medication review

Other assessments are not required at such dose adjustment visits, but are permitted, based on the Investigator's judgment.

No dose decreases are allowed prior to Day 8.

12. SAFETY REPORTING

12.1. Definitions

12.1.1. Adverse Events

An adverse event (AE) is any untoward medical occurrence associated with the use of a drug in humans, whether or not considered drug related.

Untoward medical occurrences that occur between the time of signing the informed consent form (ICF) and first drug administration are pre-treatment events. Those that occur after first administration of study drug are considered AEs.

An AE can, therefore, be any unfavorable and unintended sign (including an abnormal laboratory finding), symptom, or disease occurring after the administration of a medicinal (investigational) product, whether or not considered related to the medicinal (investigational) product. AEs may include the onset of new illness and the exacerbation of pre-existing conditions. AEs will be collected from the signing of the ICF to the last study visit (including Follow-up Visit for those not enrolling in open-label extension).

The Investigator should attempt to establish a diagnosis of the event based on signs, symptoms, and/or other clinical information. In such cases, the diagnosis should be documented as the AE and not the individual signs/symptoms.

If a subject answers "yes" to "Suicidal Ideation" Item 4 (active suicidal ideation with some intent to act, without specific plan) or Item 5 (active suicidal ideation with specific plan and intent) on any post-Baseline C-SSRS assessment, an associated AE must be reported.

12.1.2. Serious Adverse Events

A serious adverse event (SAE) is an AE that meets one or more of the following criteria:

- Results in death.
- Is life-threatening.
- Requires hospitalization or prolongation of existing hospitalization.
- Results in persistent or significant disability or incapacity.
- Is a congenital anomaly or birth defect.
- Is an important medical event that may jeopardize the subject or may require a medical or surgical intervention to prevent one of the outcomes listed above.

Examples of such medical events include allergic bronchospasm requiring intensive treatment in an emergency room or at home, blood dyscrasias or convulsions that do not result in inpatient hospitalization.

The term "severe" is often used to describe the severity of a specific event (as in mild, moderate, or severe myocardial infarction) (see [Section 12.3](#)); the event itself, however, may be of relatively minor medical significance (such as severe headache). This is not the same as "serious," which is based on subject/event outcome or action criteria usually associated with events that pose a threat to a subject's life or functioning as defined by the criteria above.

During the study, if a subject has a hospitalization or procedure (eg, elective surgery) that was scheduled before the study entry, ie, before informed consent for an event/condition that occurred before the study, the hospitalization is considered a therapeutic intervention and not the result of a SAE. However, if the event/condition worsens during the study, it should be reported as an AE (or SAE, if the event/condition results in a serious outcome such as prolongation of hospitalization).

Life-threatening means that the subject was, in the view of the Investigator, at immediate risk of death from the event as it occurred. This definition does not include an event that had it occurred in a more severe form might have caused death.

SAE criteria information will be captured on the CRF.

12.2. Objective Findings

Any clinically significant changes from Screening in objective findings (eg, clinical laboratory value, ECG value, vital sign values and physical / neurological examination observation), as determined by the Investigator, will be recorded as AEs.

When a clear diagnosis is available that explains the objective findings, this diagnosis will be recorded as the AE, and not the abnormal objective finding (eg, viral hepatitis will be recorded as the AE, not transaminase elevation). If a definite diagnosis is not available, then record the sign (eg, clinically significant elevation of transaminase levels) or symptom (eg, abdominal pain) as the AE.

Clinical laboratory test results and ECG tracings and over-read reports will be reviewed, signed and dated by the Investigator. The Investigator must determine the clinical significance of all out of range values for clinical laboratory tests and all abnormal ECG findings.

Any clinical laboratory value outside the normal range and any centrally over-read abnormal ECG finding will be flagged for the attention of the Investigator or appropriate designee at the study center. The Investigator or appropriate designee will indicate whether the value/finding is of clinical significance. Subjects with any clinically significant abnormal laboratory value(s) or ECG finding at Screening will **not** be allowed into the study (see [Section 8.2](#)). Retesting is allowed during the Screening Period and the retest used to determine eligibility after approval from the Medical Monitor. If a clinically significant laboratory or ECG abnormality is found after Screening, during the study, and/or at the Follow-Up Visit, this should be recorded as an AE and the subject will be followed until the test(s) has (have) normalised or stabilised. Possibly drug-related or clinically relevant abnormal values of uncertain causality or clinical significance must be repeated. Additional laboratory and ECG testing during the study may be performed if medically indicated.

12.3. Collection and Recording of Adverse Events

All pre-treatment events and AEs must be recorded in the subject's study records/source documents in accordance with the Investigator's normal clinical practice. Pre-treatment events and AEs and SAEs that occur from the signing of informed consent to the subject's last study visit must be recorded on the CRF. Determination of whether an event is a pre-treatment event, or an adverse event will be made programmatically by the Sponsor or designee, not by the site.

All AEs will be followed until resolution, stabilization of the condition, the event is otherwise explained, or the subject is lost to follow-up.

Each AE is to be evaluated for duration, severity, frequency, seriousness, action taken with the study treatment, outcome, and causal relationship to the study treatment. Additional information will be collected for the non-serious psychiatric AEs that led to discontinuation from the study as well as all serious psychiatric AEs within the study. Definitions for severity, frequency, action taken with the study treatment, outcome, and causal relationship to the study treatment are presented below.

The severity of AE:

- **Mild** - Ordinarily transient symptoms that do not influence performance of subject's daily activities. Other treatment is not ordinarily indicated.
- **Moderate** - Marked symptoms sufficient to make the subject uncomfortable. Moderate influence on performance of subject's daily activities. Other treatment may be necessary.
- **Severe** - Symptoms cause considerable discomfort. Substantial influence on subject's daily activities. May be unable to continue the study, and other treatment may be necessary.

The frequency of AE:

- **Once** – an isolated episode.
- **Intermittent** – occurs on two or more separate occasions.
- **Continuous** – does not abate from date of onset to date of resolution.

The action taken with the study treatment:

- **Drug Interrupted** – Study drug stopped temporarily.
- **Drug Withdrawn** – Study drug stopped permanently.
- **Dose Reduced**
- **Dose Increased**
- **Dose Not Changed**
- **Not Applicable**
- **Unknown**

The outcome of the AE:

- **Recovered/Resolved**
- **Recovering/Resolving**
- **Not Recovered/Not Resolved**
- **Recovered/Resolved with Sequelae**
- **Fatal**

- **Unknown**

The causal relationship of the AE to the study treatment:

- **Not related**

- **Not related** - Improbable temporal relationship and is plausibly related to other drugs or underlying disease.

- **Related**

- **Possible** - occurred in a reasonable time after study drug administration but could be related to concurrent drugs or underlying disease.
 - **Probable** - occurred in a reasonable time after study drug administration, is unlikely to be attributable to concurrent drugs or underlying disease, and there is a plausible mechanism to implicate the study drug.
 - **Definite** - occurred in a reasonable time after study drug administration and cannot be explained by concurrent drugs or underlying disease. The adverse event should respond to dechallenge/rechallenge however, this is not mandatory before assigning a definite causality.

The Medical Monitor is the initial contact person for protocol related questions or discussion of AEs. The contact information for the Medical Monitor as well as other emergency contact information can be found in [Table 1](#) of this protocol.

